12.2.2 Sensitivity Analyses

As sensitivity analyses to the imputation method used for the main analysis of the vIGA-AD endpoints (refer to Section 12.2.1), the main analysis of these endpoints will be repeated, but using the following imputation method:

- Non-responder imputation (refer to Section 6.2.2)
- Observed cases (i.e., no imputation)

No sensitivity analyses will be performed for the secondary efficacy endpoints based on WI-NRS and EASI total score.

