5.5 Derived Variables

All questionnaire scores will be derived by Biostatistics in the ADaM datasets using the formulas defined below, even if calculated scores are present in the EDC database. All pre-calculated scores will be ignored for analysis.

- With the following exception, vIGA-AD Score of Clear (0) or Almost Clear (1) = vIGA-AD of ‘Clear’ (0) or ‘Almost Clear’ (1). The exception is that for subjects who discontinued early from study due to an AE or lack of efficacy, the subject will be considered as not having a vIGA-AD score of Clear (0) or Almost Clear (1) for all pre-specified analysis visits (refer to Section 5.4) for which the subject’s day of last dose falls within or is before the start of the analysis visit window.
- With the following exception, vIGA-AD Success = vIGA-AD of ‘Clear’ (0) or ‘Almost Clear’ (1) plus at least a 2-grade improvement from baseline. The exception is that for subjects who discontinued early from study due to an AE or lack of efficacy, the subject will be considered as not having a vIGA-AD success for all pre-specified analysis visits (refer to Section 5.4) for which the subject’s day of last dose falls within or is before the start of the analysis visit window. vIGA-AD Success will be derived for both the Primary and OLE baselines (refer to Section 5.2)
- Date of last contact = the latest of last study visit date, last dose date, end-of-study date and end-of-treatment date.
- Post-OLE Week 4 study duration (days): The duration can be represented as End Date – Start Date +1. The start date of the Post-OLE Week 4 interval will be the date of the OLE Week 4 visit or OLE Day 29 if the subject missed the OLE Week 4 visit. The end date will be the date of last contact. This endpoint will be calculated only for subjects who enter the post-OLE Week 4 study period.
- Duration (days) of the first BIW dosing will be calculated from the first BIW dosing to the start of the succeeding QD dosing interval. Subject’s last contact date will be used to censor

 Innovaderm Research	STATISTICAL ANALYSIS PLAN, Final Version 1.0
Protocol Number: ARQ-151-313	Sponsor: Arcutis Biotherapeutics, Inc.

this endpoint (time-to-event analysis) or as the end date of this duration (analyzed as a continuous endpoint) for subjects who do not revert to a QD dosing regimen after the first BIW dosing. This endpoint will be calculated only for subjects who enter the post-OLE Week 4 study period with at least one BIW dosing interval.

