Note: Palms and soles may be treated with investigational product in this study, but will not be counted towards IGA, EASI, or BSA assessments. EASI is evaluated for the entire body except the scalp, palms, and soles.

Note: If a subject turns 8 years old during the study, the formula used at Screening of the preceding study will continue to be used through the duration of the subject's participation in this study.

- EASI-50, EASI-75, EASI-90, EASI-100 - Achievement of at least a 50%, 75%, 90%, or 100% reduction from baseline in the EASI total score.
- DLQI Total Score = sum of the 10 questions (individual questions scored as Very much=3, A lot=2, A little=1, Not at all=0, Not relevant=0, Question 7: Yes=3, if No, then follow the same score as A lot, A little, Not at all), ranging from 0 to 30. If 1 item is missing, it is scored as 0 for that item. If 2 or more items are missing, the score should not be calculated. The DLQI will be performed for the subject with age 17+ years based on age at start of preceding studies ARQ-151-311/312/315.
- CDLQI Total Score = sum of the 10 questions (individual questions scored as Very much=3, Quite a lot=2, Only a little=1, Not at all=0; Question 7: if the last week was school time, the question was scored as Very much=3, Quite a lot=2, Only a little=1, Not at all=0, with Prevented school recoded to 3, and if the last week was holiday time, the standard responses apply), ranging from 0 to 30. If 1 item is missing, that item is scored as 0. If 2 or more items are missing, the score should not be calculated. The CDLQI will be performed for the subjects with age >4 and <16 years based on age at start of preceding studies ARQ-151-311/312/315.

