12 EFFICACY ANALYSES

Unless otherwise indicated, missing efficacy data will not be imputed.

Efficacy endpoints will be summarized based on the full analysis set. For change and percent change efficacy endpoints relative to baseline, summaries will be performed relative to both Primary Baseline and OLE Baseline (refer to Section 5.2).

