12.2.1 Main Analysis

Missing vIGA-AD secondary efficacy endpoints will be imputed as described in Section 6.2.1. The combined common proportion of subjects achieving each vIGA-AD secondary endpoint will be provided by visit and treatment group (refer to Section 5) along with their combined common two-sided 95% CI. The vIGA-AD success summaries based on the OLE Baseline (refer to Section

 Innovaderm Research	STATISTICAL ANALYSIS PLAN, Final Version 1.0
Protocol Number: ARQ-151-313	Sponsor: Arcutis Biotherapeutics, Inc.

5.2) will only include subjects who have an OLE baseline score other than clear (0) or almost clear (1).

The change and percent change from baseline in WI-NRS score will be summarized among subjects 12 years or older at the start of the parent study* using descriptive statistics by visit and treatment group (refer to Section 5) based on observed cases (i.e., no imputation). Two-sided 95% CI of the mean will also be provided. WI-NRS score will be summarized similarly.

* WI-NRS score, change from baseline and percent change from baseline for subjects < 12 years old at the start of the parent study will be summarized in subgroup analysis (refer to Sections 6.6 and 12.2.3).

The change and percent change from baseline in EASI total score will be summarized using descriptive statistics by visit and treatment group (refer to Section 5) based on observed cases (i.e., no imputation). Two-sided 95% CI of the mean will also be provided. EASI total score will be summarized similarly.

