12.3.1 Main Analysis

Missing other efficacy endpoints will not be imputed.

Duration, cumulative time, and percent of time endpoints will be summarized using descriptive statistics by treatment group (refer to Section 5) and two-sided 95% CI of the mean will also be provided.

For duration endpoints, the number and percentage of subjects experiencing a status change or censored will be provided overall and by treatment group, along with reason for censoring. Additionally, these endpoints will also be analyzed using Kaplan–Meier (KM) method. The KM estimates of the time-to-event will be provided overall and by treatment group for the 25th, 50th (median), and 75th percentiles along with their corresponding two-sided 95% CI. The estimates of the SEs will be computed using the Greenwood's formula. The two-sided 95% CI for the survival function at the 25th, 50th, and 75th percentiles will be calculated according to Brookmeyer and Crowley (1982)². KM curves will be provided overall and by treatment group.

Dichotomic, change from baseline, and percent change from baseline endpoints will be summarized similarly as the secondary efficacy endpoints (refer to Section 12.2).

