12.3.2 Sensitivity Analyses

No sensitivity analyses will be performed for the other efficacy endpoints.

 Innovaderm Research	STATISTICAL ANALYSIS PLAN, Final Version 1.0
Protocol Number: ARQ-151-313	Sponsor: Arcutis Biotherapeutics, Inc.

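### EASI and itch endpoints use observed cases only, with no discontinuation rule or sensitivity analysis, unlike the vIGA-AD responder endpoints, so late-visit results may overstate long-term efficacy

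*SAP*

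**What the plan says.** **EASI and WI-NRS change (secondary).** The general rule in SAP section 12 is "Unless otherwise indicated, missing efficacy data will not be imputed". Section 12.2.1 follows it: "The change and percent change from baseline in EASI total score will be summarized using descriptive statistics by visit and treatment group", using observed values only. WI-NRS change is handled the same way. Section 12.2.2 adds: "No sensitivity analyses will be performed for the secondary efficacy endpoints based on WI-NRS and EASI total score".

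**EASI-50/75/90/100 and WI-NRS 4-point response (other efficacy).** Section 12.3.1 states "Missing other efficacy endpoints will not be imputed", and section 12.3.2 states "No sensitivity analyses will be performed for the other efficacy endpoints". The EASI responder definition in section 5.5 is only "Achievement of at least a 50%, 75%, 90%, or 100% reduction from baseline in the EASI total score". Neither it nor the WI-NRS response definition has an exception for discontinuation.

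**vIGA-AD 0/1 and vIGA-AD success (secondary).** Section 5.5 does have such an exception. When someone stops early because the treatment did not work or because of an adverse event (AE), "the subject will be considered as not having a vIGA-AD score of Clear (0) or Almost Clear (1) for all pre-specified analysis visits" whose window contains, or starts after, the last dose. The same applies to vIGA-AD success. Section 6.2.1 removes those subjects' data from the affected windows, citing the parent studies' primary estimand, and multiply imputes what is missing. Sections 6.2.2 and 12.2.2 add non-responder imputation and observed cases as sensitivity analyses.

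**The concern.** EASI, itch and vIGA-AD measure the same disease in the same subjects, yet a subject who stops because the cream failed is treated differently in each. For the vIGA-AD responder endpoints that subject stays in as a failure. For EASI and WI-NRS the subject contributes nothing after the last available value.

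There is a plausible route for selective loss. Protocol section 4.6.1 (notes to Table 2) permits no rescue therapy, and section 4.7.6 lists a need for prohibited medication as a ground for removal. If poorly controlled subjects leave more often, observed-case response rates and mean changes improve over time through selection.

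Two secondary endpoints and the EASI and itch responder rates are affected. EASI-50, EASI-75 and WI-NRS endpoints are also carried into subgroup analyses (SAP section 6.6).

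**Working it through.** The documents state no response rate, dropout rate or mix of dropout reasons, so there is no planned figure to reproduce. The check is a case traced through the SAP's own rules, followed by an illustration on assumed inputs.

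**Traced case.** Take a Cohort-Week 52 subject who stops for lack of efficacy, with last dose on Day 59 and early termination (ET) visit on Day 60. Under SAP section 5.4, Table 3, the Week 12 window is Days 58–127. With no scheduled Week 12 value, the ET value is used there.

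| Visit | vIGA-AD 0/1 and success | EASI-75 |
|---|---|---|
| Week 12 | Failure, whatever the ET score | ET value counts, as a response if the reduction is at least 75% |
| Weeks 24, 36, 52 | Failure | No value; on the observed-case reading, out of the denominator |

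A subject stopping for an AE on the same days is treated identically.

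**Responder illustration (all inputs assumed).** Let p be the response rate among those observed, d the share with no value at the visit because they left, and f the share of leavers who left for an AE or lack of efficacy.

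- Observed case reports p at any d.
- Non-responder imputation (NRI) gives p(1 − d), a gap of p·d.
- Failing only AE and lack-of-efficacy leavers and imputing the others at p gives p(1 − d) + d(1 − f)p, a gap of p·d·f.

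With p = 70%:

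| d | NRI | Gap p·d | Gap p·d·f, f = 25% | Gap p·d·f, f = 50% |
|---|---|---|---|---|
| 15% | 0.70 × 0.85 = 59.5% | 10.5 points | 2.6 | 5.3 |
| 25% | 0.70 × 0.75 = 52.5% | 17.5 points | 4.4 | 8.8 |
| 35% | 0.70 × 0.65 = 45.5% | 24.5 points | 6.1 | 12.3 |

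The extremes of the last two columns are 0.70 × 0.15 × 0.25 = 2.6 points and 0.70 × 0.35 × 0.50 = 12.3 points.

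**Mean-change illustration (assumed).** If those observed average −75% in EASI and leavers would have averaged m, the all-subject mean is (1 − d)(−75) + d·m. At d = 20%, m = −75 gives −75% and m = 0 gives 0.8 × (−75) = −60%. The observed-case table shows −75% in both cases.

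**Denominator.** For the responder endpoints, section 12.3.1 excludes imputation but also says dichotomous endpoints are summarised like the secondary ones, whose main analysis is multiple imputation. The default in Appendix 1 makes the percentage denominator the whole population in the treatment group unless specified otherwise. Read literally, that default would count every missing subject as a non-responder, including Cohort-Week 24 subjects at Weeks 36 and 52, who left by design. Leaving the denominator is the natural reading, but the SAP does not settle it.

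**The case against.** **The SAP does not contradict itself.** A reader might infer a contradiction with the vIGA-AD handling. The documents do not support that: section 12 sets no imputation as the default, and section 12.2.1 openly departs from it for the vIGA-AD responder endpoints. Change in vIGA-AD score is itself unimputed, so the line is not simply vIGA-AD against EASI. What stands is an unexplained inconsistency.

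**Upward bias is not shown.** A reader might also infer that the EASI and itch results will certainly be inflated. No dropout rate or reason mix is given, and subjects can leave for reasons unrelated to response. The direction is plausible only.

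**Leavers are not wholly lost.** An ET visit includes the Week 52 procedures (protocol section 5.5) and counts in the window where it falls. A leaver seen on Day 310 or later is therefore included at Week 52 for EASI. Part of the fall in n after Week 24 is the planned exit of Cohort-Week 24.

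**The plan offers some guide to attrition.** vIGA-AD and EASI are assessed at the same visits, and the vIGA-AD responder endpoints are reported under three approaches. Reasons for discontinuation and n are also reported. So it would be wrong to say that nothing in the plan bears on the size. The guide is partial, however. The failure rule sits in the section 5.5 derivation, so it applies to the observed-case vIGA-AD table too, and the spread across the three tables does not isolate its effect.

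**Stakes are limited.** The protocol's only objective is safety, EASI and WI-NRS are descriptive, and no hypothesis tests are planned. This stands: no error rate or primary conclusion is touched.

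**Conclusion.** The point holds as an unexplained difference in handling. Under the stated rules a lack-of-efficacy or AE leaver can count as an EASI-75 response in the ET window and then be absent from later visits, while counting as a vIGA-AD failure throughout. Late-visit EASI and itch results may therefore overstate long-term efficacy.

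The size cannot be derived from the documents. At an assumed p = 70% and d = 15–35%, 10.5–24.5 points is an upper bound on the gap, because it fails every leaver. A reader might take it as the expected bias, but the vIGA-AD main approach fails only some leavers. On that approach, with f = 25–50% and the rest imputed at p, the gap is about 2.6–12.3 points. Neither range includes the further effect of recoding an ET response as a failure.

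The matter bears on interpretation of long-term efficacy and should be addressed before the efficacy tables are produced.

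**What to change.** 1. Apply the section 5.5 AE and lack-of-efficacy failure rule to EASI-50/75/90/100 and WI-NRS 4-point response.
2. Add an NRI sensitivity table for these endpoints, limited to visits each subject was due to attend. Exclude Cohort-Week 24 at Weeks 36 and 52, and visits not yet reached at an interim analysis. Section 6.2.2 has no such limit, so copying it unchanged could count planned completers as failures.
3. State the denominator for these endpoints, resolving section 12.3.1 against the Appendix 1 default, and report n by visit.
4. Optionally, add one multiple-imputation sensitivity analysis for EASI and WI-NRS change. It needs its own imputation model, because the one in section 6.2.1 is built for integer vIGA-AD scores from 0 to 4 with earlier vIGA-AD scores as predictors.

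Items 1 to 3 cost a few extra tables and a short SAP amendment; item 4 also needs model specification. The added figures will be less favourable than the observed-case ones. If the sponsor prefers observed cases alone, the SAP should say why these endpoints are treated differently.

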12.2.3 Subgroup Analyses

The main analysis of the secondary efficacy endpoints of vIGA-AD score of clear (0) or almost clear (1) and vIGA-AD success (refer to Section 12.2.1) will be repeated for each of the subgroups mentioned in Section 6.6. Subgroup analyses will only be conducted for results relative to the primary baseline only.

12.3 Other Efficacy Analyses

Other efficacy endpoints in this study are:

- Duration (days) of the first BIW dosing interval

 Innovaderm Research ■■■	STATISTICAL ANALYSIS PLAN, Final Version 1.0
Protocol Number: ARQ-151-313	Sponsor: Arcutis Biotherapeutics, Inc.

- Cumulative time (days) on BIW dosing
- Percent of time on BIW dosing
- Duration (days) of the first disease control interval
- Cumulative time (days) with disease control
- Percent of time with disease control
- Duration (days) of the first interval with vIGA-AD score of Clear (0)
- Cumulative time with vIGA-AD score of Clear (0)
- Percent of time with vIGA-AD of Clear (0)
- Duration (days) of the first interval with vIGA-AD score of Clear (0) or Almost Clear (1)
- Cumulative time with vIGA-AD score of Clear (0) or Almost Clear (1)
- Percent of time with vIGA-AD of Clear (0) or Almost Clear (1)
- Change and percent change from baseline in vIGA-AD score over time
- In subjects \geq 12 years old at the start of the parent study* with baseline WI-NRS \geq 4, achievement of at least a 4-point reduction on the WI-NRS over time
- Achievement of at least a 50%, 75%, 90%, 100% reduction in the EASI total score (EASI-50, EASI-75, EASI-90, EASI-100) over time
- Change and percent change from baseline in BSA affected by AD over time
- Change and percent change from baseline in IDQOL, CDLQI, and DLQI over time
- Change and percent change from baseline in DFI over time
- Change and percent change from baseline in SCORAD over time
- Change and percent change from baseline in POEM over time

* WI-NRS score, change from baseline and percent change from baseline for subjects $<$ 12 years old at the start of the parent study will be summarized in subgroup analysis (refer to Sections [6.6](#) and [12.2.3](#)).

 Innovaderm Research	STATISTICAL ANALYSIS PLAN, Final Version 1.0
Protocol Number: ARQ-151-313	Sponsor: Arcutis Biotherapeutics, Inc.

Endpoints that are durations, cumulative times, or percent of times are defined in Section [5.5](#) while endpoints that are not durations, cumulative times, or percent of times are based on the following scales/questionnaires/assessments/tools:

- The vIGA-AD scale (refer to Section [12.2](#))
- The WI-NRS scale (refer to Sections [5.5](#) and [12.2](#))
- The EASI questionnaire (refer to Section [12.2](#))
- Percentage of BSA affected by AD will be determined by the subject's hand method, where the subject's hand (including fingers) surface area is assumed to equal 1% of BSA (excluding the scalp, palms, soles).
- The DLQI and CDLQI questionnaires are designed to measure the health-related quality of life of patients suffering from a skin disease. The DLQI/CDLQI consists of 10 questions concerning patients' perception of the impact of skin diseases on different aspects of their health-related quality of life over the last week. The DLQI will be completed by subjects ≥ 17 years of age (based on age at start of preceding studies ARQ-151-311/312). The CDLQI will be completed for subjects ≥ 4 years of age and ≤ 16 years of age (based on age at start of preceding studies ARQ-151-311/312/315). Subjects who were assessed using CDLQI in their preceding study (ARQ-151-311/312/315) will remain on CDLQI in the current study (ARQ-151-313). DLQI/CDLQI total score will be computed as specified in Section [5.5](#).
- The IDQOL questionnaire is designed to assess the impact of AD on the quality of life of infants below the age of four years (≤ 4 years). Subjects who were assessed using IDQOL in their preceding study (ARQ-151-315) will remain on IDQOL in the current study (ARQ-151-313). It should be completed by the child's parent(s) or regular caregiver. IDQOL score will be computed as specified in Section [5.5](#).
- The DFI questionnaire measures how much having a child with AD affects the quality of life of other (adult) members of the family. It will be completed by parents/guardians/caregivers for subjects ≤ 17 years of age. DFI is not to be conducted for subjects who were ≤ 17 years of age in the ARQ-151-311/312 studies and turned 18 years of age prior to enrollment into ARQ-151-313. DFI total score and subscale scores will be computed as specified in Section [5.5](#).
- The SCORAD clinical tool assesses the severity (i.e., extent, intensity) of AD as objectively as possible. First, the overall %BSA affected by AD is evaluated (from 0% to

 Innovaderm Research ■■■	STATISTICAL ANALYSIS PLAN, Final Version 1.0
Protocol Number: ARQ-151-313	Sponsor: Arcutis Biotherapeutics, Inc.

100%, where a subject's palm represents 1% of his/her total BSA). Secondly, the AD severity is evaluated based on 6 items (erythema, edema/papulation, oozing/crusts, excoriation, lichenification, and dryness) graded using a 4-point scale (half steps are not allowed): 0 (absence), 1 (mild), 2 (moderate), and 3 (severe). Lastly, 2 subjective items (loss of sleep and intensity of pruritus) are evaluated by having the subject indicates on a 10.0 cm visual analog scale (VAS) the point corresponding to the average value over the last 3 days (0 cm = none to 10 cm= maximum). SCORAD total score will be computed as specified in Section 5.5.

- The POEM tool is used to monitor AD severity. It focuses on the illness as experienced by the subject. It consists of a 5-point scale measuring the frequency of each of 7 AD symptoms (i.e., dryness, itching, flaking, cracking, sleep loss, bleeding, and weeping) over the past week scored from 0 (no days), 1 (1 to 2 days), 2 (3 to 4 days), 3 (5 to 6 days), and 4 (every day). POEM total score will be computed as specified in Section 5.5.

12.3.1 Main Analysis

Missing other efficacy endpoints will not be imputed.

Duration, cumulative time, and percent of time endpoints will be summarized using descriptive statistics by treatment group (refer to Section 5) and two-sided 95% CI of the mean will also be provided.

For duration endpoints, the number and percentage of subjects experiencing a status change or censored will be provided overall and by treatment group, along with reason for censoring. Additionally, these endpoints will also be analyzed using Kaplan–Meier (KM) method. The KM estimates of the time-to-event will be provided overall and by treatment group for the 25th, 50th (median), and 75th percentiles along with their corresponding two-sided 95% CI. The estimates of the SEs will be computed using the Greenwood's formula. The two-sided 95% CI for the survival function at the 25th, 50th, and 75th percentiles will be calculated according to Brookmeyer and Crowley (1982)². KM curves will be provided overall and by treatment group.

Dichotomic, change from baseline, and percent change from baseline endpoints will be summarized similarly as the secondary efficacy endpoints (refer to Section 12.2).

